11.1.5.6. Blood loss using changes in hematocrit following eschar removal procedures

The measure of blood loss defined in Section 10.3.5.12 will be computed for each patient, analyzed descriptively with number of units, number of missing values, mean, standard deviation, min, max, median and quartiles as shown in Table 4 and compared between groups with a one way analysis of variance. A graphical representation of the data will be done using histograms.

11.1.5.7. Blood loss using changes in hemoglobin following eschar removal procedures

The measure of blood loss defined in Section 10.3.5.13 will be computed for each patient, analyzed descriptively with number of units, number of missing values, mean, standard deviation, min, max, median and quartiles as shown in Table 4 and compared between groups with a one way analysis of variance. A graphical representation of the data will be done using histograms.

11.1.5.8. Blood loss in NexoBrid procedures vs. surgical procedures

The measure of blood loss defined in Section 10.3.3.3.1 will be computed for each procedure, and analyzed descriptively with number of procedures, number of missing values, mean, standard deviation, min, max, median and quartiles as shown in Table 4 and compared between NexoBrid procedures and surgical procedures with a one way analysis of variance. A graphical representation of the data will be done using histograms.

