9.2. Secondary Endpoint: Incidence of surgical excision

Estimated proportions having surgical excision from study MW2004-11-02: NexoBrid 0.22; SOC 0.62

Standard errors: NexoBrid 0.048; SOC 0.054

Difference = 0.40; Standard error of difference = 0.072

Anticipated difference: $0.40 - 0.072/2 \approx 0.36$

We therefore take the anticipated proportion with complete excision to be: NexoBrid 0.24 and SOC 0.60.

Using Fisher's exact test, the sample size needed to achieve 90% power using a two-sided significance level of 5% is **86**: 43 in the NexoBrid group and 43 in the SOC group.

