10.3.3.3. Secondary Endpoint: Blood loss

10.3.3.3.1. Blood loss for main analysis

For each patient and each procedure carried out to remove eschar the estimated blood volume (EBV) will be calculated as

$$EBV = 70 \frac{cm^3}{kg} * weight(kg)$$

Furthermore, the total volume of whole blood and packed red blood cells (PRBC) transfused (in milliliters) will be calculated per procedure (transfusions given during the procedure and 4 hours \pm 15 minutes later) and denoted by V_{WB} and V_{PC} in the following.

From these quantities, the blood loss (Actual Blood Loss, ABL) will be calculated using the following formula [25]:

$$ABL = \frac{EBV * (Hb_{before} - Hb_{after})}{(Hb_{before} + Hb_{after})/2} + V_{WB} + \frac{5}{3}V_{PC}$$

The factor of 5/3 is derived from chapter 5 of Transfusion Medicine, 4th Edition [31] and compensates for the fact that equal volumes of whole blood and packed red blood cells are not comparable.

The ABL will be summed over all procedures carried out to remove eschar, with the Hb measured immediately before each procedure and 4 hours after its completion. The amount of blood transfused will be summed over all transfusions carried out during the debridement procedure and 4 hrs later i.e. the before-after periods that are spanned by these Hb measurements.

Additionally, blood loss will be computed considering the whole debridement process as one continuous procedure. For this value, the formula for ABL given above will also be used. However, the ABL will be computed using the Hb measured immediately before the first procedure and 4 hours after completion of the last procedures. The amount of whole blood and packed red blood cells (PRBC) transfused will be calculated as before, but incorporating all such transfusions in the time frame spanned by the Hb measurements used for the calculation (pre first procedure to 4 hrs post last procedure (in which complete debridement was achieved).

Analyses with both blood loss values will be conducted. However, some missing values are expected. The analysis with less missing values will be regarded as more reliable and is therefore considered the main analysis. The other analysis is considered supportive.

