10.3.3.3.5. Course of debridement procedure

For the multiple imputation outlined in Section 10.1.1.3 for each patient a categorical variable describing the course of the debridement process will be calculated. The different levels of the variable are defined as:

- Only non-surgical SOC debridement
- Non-surgical SOC debridement followed by surgical debridement
- Only surgical debridement
- Only NexoBrid debridement
- NexoBrid debridement followed by non-surgical SOC debridement followed by surgical debridement
- NexoBrid debridement follow by surgical debridement
- Only Gel Vehicle debridement
- Gel Vehicle debridement followed by non-surgical SOC debridement followed by surgical debridement
- Gel Vehicle debridement followed by surgical debridement

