10.3.4.2. Safety Endpoint: Cosmesis and function at 12 months from wound closure

MVSS sub scores at 12 months for pigmentation, pliability, height, vascularity, pain and pruritus will be added up to obtain the overall MVSS score (range 0 to 18) at 12 months per target wound. The patient MVSS score will be the average of the MVSS over all TWs. Additionally, the average MVSS score for donor site scars will be calculated per patient.

10.3.4.3. *Safety Endpoint: Cosmesis and function at 24 months from wound closure*

MVSS sub scores at 24 months for pigmentation, pliability, height, vascularity, pain and pruritus will be added up to obtain the overall MVSS score (range 0 to 18) at 24 months per target wound. The patient MVSS score will be the average of the MVSS over all TWs. Additionally, the average MVSS score for donor site scars will be calculated per patient.

10.3.4.4. *General Parameters of safety*

Volume of blood transfusions given

The volume of blood transfusions given during hospitalization will be computed for each patient as $V_{WB} + \frac{5}{3}V_{PC}$, where V_{WB} and V_{PC} are the volume (in milliliters) of whole blood and packed red blood cells transfused. As in the calculation of blood loss in Section 10.3.3.3.1, the factor of 5/3 is derived from chapter 5 of Transfusion Medicine, 4th Edition [31] and compensates for the fact that equal volumes of whole blood and packed red blood cells are not comparable.

The volume of blood transfused will be calculated overall, as well as separately for volumes transfused before start of treatment, during the ER period, within 1 week after the ER period and later than 1 week after the ER period for each patient.

Extent of analgesia, anesthesia and antibiotic use

The numbers and percentages of patients per each level of sedation (see definitions in Appendix 13.1.2) per procedure (in topical arms: 1st and second topical application, surgical rescue procedures and non-surgical rescue procedures; in SOC arms: surgical procedures and non-surgical procedures) will be calculated.

The number of days of exposure to antibiotic drugs will be calculated for each patient. This will be done overall, for antibiotic use due to AE involvement (as indicated in the eCRF) and for prophylactic antibiotic use (as indicated in the eCRF) separately.

Incidence of increased interstitial/compartment syndrome

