10.3.5.12. *Blood loss using changes in hematocrit following eschar removal procedures*

For each debridement procedure, the change in hematocrit will be calculated as the difference of the hematocrit value before the procedure and the hematocrit value 4 hours post the procedure. This difference in hematocrit values will be summed for each patient.

Furthermore, for each patient, the difference of the hematocrit value prior to the first debridement procedure and the hematocrit value 4 hours post the last debridement procedure will be calculated.

10.3.5.13. *Blood loss using changes in hemoglobin following eschar removal procedures*

For each debridement procedure, the change in hemoglobin will be calculated as the difference of the hemoglobin value before the procedure and the hemoglobin value 4 hours post the procedure. This difference in hemoglobin values will be summed for each patient.

Furthermore, for each patient, the difference of the hemoglobin value prior to the first debridement procedure and the hemoglobin value 4 hours post the last debridement procedure will be calculated.

10.3.5.14. *Blood loss comparing NexoBrid procedures to surgical procedures*

For a comparison of blood loss between NexoBrid procedures and surgical procedures, the blood loss per eschar removal procedure will be calculated as outlined in Section 10.3.3.3.1.

10.3.5.15. *Autograft related parameters*

The total number of grafting procedures per patient and per target wound will be computed. Procedure will be based on the date in the eCRFs per patient and per wound.

Furthermore, a binary (yes/no) variable will be computed indicating whether more than one autografting procedure was performed on a wound level as well as on a patient level.

The area of repeat autografting for each wound will be calculated as follows:

$$Area_{repeat} = \sum_{i=2}^n Area_i,$$

where n is the total number of autografting procedures for the specific wound and $Area_i$ is the area autograft in the i-th grafting procedure for that wound.

The area of repeat autografting on a patient level is calculated as the sum over the areas of repeat grafting over all TWs of that patient.

10.3.5.16. *Duration of hospitalization*

Duration of acute hospitalization will be computed as the difference in days between hospital admission and hospital discharge (initial hospitalization only).

10.3.5.17. *Time to reach 100% wound closure*

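### The exploratory procedure-level blood-loss comparison (SAP 11.1.5.8) does not restrict its surgical group to an arm, and its one-way ANOVA treats overlapping within-patient procedures as independent

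*SAP*

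**What the plan says.** SAP 11.1.5.8, under the first-stage exploratory analyses, fixes the unit: "The measure of blood loss defined in Section 10.3.3.3.1 will be computed for each procedure". The values are then to be "compared between NexoBrid procedures and surgical procedures with a one way analysis of variance". The derivation in 10.3.5.14 is equally short: "For a comparison of blood loss between NexoBrid procedures and surgical procedures, the blood loss per eschar removal procedure will be calculated", with a pointer to 10.3.3.3.1. None of these sentences names a treatment arm.

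The measure itself has the widest scope. Section 10.3.3.3.1 opens: "For each patient and each procedure carried out to remove eschar the estimated blood volume (EBV) will be calculated". Section 10.3.3.3.5 lists the courses of debridement that the plan expects, among them "NexoBrid debridement follow by surgical debridement" and "Gel Vehicle debridement followed by surgical debridement".

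In one place the plan does label surgery by arm. For the sedation analysis (10.3.4.4, repeated in 11.1.4.14), the topical arms have "surgical rescue procedures and non-surgical rescue procedures; in SOC arms: surgical procedures and non-surgical procedures".

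The secondary blood-loss endpoint is built differently. It sums loss over all eschar removal procedures of a patient (10.3.3.3.1) and compares the NexoBrid group with the SOC group (11.1.3.3) in the full analysis set, by planned treatment (9.5).

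**The concern.** The two groups are defined by what was done, not by the arm to which the patient was randomised. Surgery after an incomplete topical debridement is an eschar removal procedure and it is surgical, so on the plain wording it belongs to the surgical group. A NexoBrid patient who goes on to excision then supplies values to both sides of the contrast. A patient with several procedures of one type supplies several values to one side.

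Two things follow. First, the surgical mean is a mixture of SOC surgery and rescue surgery in unstated proportions, so it is unclear what the contrast estimates. Second, one-way ANOVA assumes independent observations, which these are not. By the general rule in sections 11 and 11.1.8 the test is read at the two-sided 0.05 level, so a p-value with no valid basis would appear in the report.

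**Working it through.** **Inputs**
- Anticipated surgery rates (9.2): "NexoBrid 0.24 and SOC 0.60". Prior-study rates in the same section: 0.22 and 0.62.
- Planned arm sizes (9.3.1): 75 NexoBrid, 75 SOC, 25 Gel Vehicle.
- Assumed, because the SAP gives no figure: one operation per operated patient; a surgery rate in the Gel arm from 0 to 1; and r, the mean loss per rescue operation divided by the mean loss per SOC operation, from 0.5 to 1.5.

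**1. The plan's own figure.** The SAP gives no sample size or effect size for any blood-loss comparison. The nearest figure is the 43 per group for surgical excision, from which the rates are taken. With mean rate 0.42 and difference d = 0.36:

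n = [1.96 × √(2 × 0.42 × 0.58) + 1.28 × √(0.24 × 0.76 + 0.60 × 0.40)]² / 0.36², which rounds up to 38 per group.

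With the continuity correction this becomes 43. Exact enumeration of Fisher's test at 43 per group gives power 0.904. The figure reproduces.

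**2. Who is in the surgical group.**
- NexoBrid: 75 × 0.24 = 18 operated patients.
- SOC: 75 × 0.60 = 45 operated patients.
- NexoBrid share in these two arms: 18 / (18 + 45) = 18/63 = 29%. With the prior-study rates: 16.5/63 = 26%.
- Adding Gel at an assumed rate of 0.60: (18 + 15) / (63 + 15) = 33/78 = 42% from the topical arms. At an assumed rate of 1: (18 + 25) / (63 + 25) = 43/88 = 49%.

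These are shares of patients. They become shares of procedures only under the assumption of one operation each.

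**3. Effect on the surgical mean.** Set the SOC operation mean to 1. The pooled mean is (S + r × R) / (S + R), with S SOC operations and R rescue operations.

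| | r = 0.5 | r = 1 | r = 1.5 |
|---|---|---|---|
| NexoBrid rescues only (S = 45, R = 18) | 0.86 | 1.00 | 1.14 |
| With Gel rescues at 0.60 (S = 45, R = 33) | 0.79 | 1.00 | 1.21 |

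Against an SOC-only comparator, pooling widens the contrast in NexoBrid's favour if r is above 1, narrows it if r is below 1, and leaves it unchanged at r = 1.

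**4. Effect on the standard error.** Let ρ be the within-patient correlation of procedure values.
- *Overlap between groups.* With one NexoBrid procedure in each of 75 patients, 63 operations and 18 patients on both sides, the covariance of the two means is 18ρσ² / (75 × 63) = 0.0038ρσ². The ANOVA variance is σ²(1/75 + 1/63) = 0.0292σ². It is too large by the fraction 2 × 0.0038ρ / 0.0292 = 0.26ρ.
- *Repeats within a group.* If each patient supplies m procedures to a group, the variance of that group's mean is 1 + (m − 1)ρ times what ANOVA takes it to be, so ANOVA is too small.

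With positive ρ the two effects pull in opposite directions. The SAP gives neither ρ nor the number of procedures per patient, so the net error cannot be signed in advance. It is zero only if ρ is zero or the two happen to cancel.

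**The case against.** **An SOC-only reading is possible.** The SAP never states that rescue surgery is in the comparator, and the sedation wording uses a separate label for it. This stands in part: inclusion follows from an unrestricted phrase. But the blood-loss imputation in 10.1.1.3 uses surgical versus non-surgical as a procedure attribute and fits the model within each treatment group, so there surgery is not confined to SOC. The flow chart (Table 1) also puts additional procedures in the topical arms under the SOC-procedure column. If SOC only was meant, the text still has to say so.

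**A reader might infer that the analysis favours NexoBrid,** because bleeding after NexoBrid failure is moved to its comparator. The documents do not support this as a statement about the mean contrast. Step 3 shows that the sign depends on r, which the SAP does not give, and surgery on a partly cleared wound could bleed less. Gel rescue surgery is not bleeding after NexoBrid failure at all. Repeated NexoBrid applications spread loss over more records, but 7.1.1.2 allows SOC procedures to be repeated too. The allocation does omit rescue bleeding from the NexoBrid side, but the secondary endpoint charges it there.

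**The question is legitimate and the stakes are low.** How much one application bleeds compared with one excision is a fair descriptive question, and both headings already speak of procedures. The analysis is exploratory and outside the four-step hierarchy of 11.1.8. All of this stands, and it limits the weight of the point. It does not rescue the test: even with SOC surgery alone as comparator, repeated procedures within a patient remain dependent.

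**Conclusion.** The point holds as a minor one on an exploratory analysis. The surgical group in 11.1.5.8 is not restricted to an arm, so on the plain wording it can take rescue surgery from the topical arms. At the plan's rates, 18 of 63 operated NexoBrid and SOC patients (29%) would come from the NexoBrid arm and appear on both sides. With Gel surgery anywhere from none to all, 29% to 49% of operated patients would come from the topical arms. These figures rest on the anticipated rates, the full planned enrolment and an assumed Gel rate. They describe the make-up of the group and do not measure bias.

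The firm statistical conclusion is that one-way ANOVA is the wrong test for repeated and overlapping procedures, so its standard error and p-value are not valid. The direction of any shift in the mean contrast is unknown. The main blood-loss conclusion is untouched, because 11.1.3.3 compares patient totals by planned treatment.

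**What to change.** In 10.3.5.14 and 11.1.5.8:
- Show three groups of procedures: NexoBrid procedures, SOC-arm surgery and topical-arm rescue surgery. Make SOC-arm surgery the comparator.
- Replace the one-way ANOVA with a linear mixed model with a random patient effect and area treated as a covariate.
- Label the result a non-randomised procedure-level comparison, and refer to 11.1.3.3 as the comparison that counts rescue bleeding by arm.

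The cost is a few sentences in the SAP, an arm indicator and slightly more programming. The interval and p-value may change, and so may the estimated difference, in either direction. The comparison stays non-randomised after the change, since SOC patients treated without surgery (about 40% at the plan's rate of 0.60) are still absent from it.

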11.1.5.9. Autograft related parameters

Total number of autografting procedures

The total number of autografting procedures (per patient) will be analyzed by displaying counts and percentages by treatment group (see Table 5). Furthermore, bar plots will be displayed. The distribution of the total number of autografting procedures will be compared between treatment groups using a chi square test (or Fisher's exact test in case of small estimated cell counts).

This analysis will be repeated on a wound level.

Incidence of repeated autografting

This is a binary (yes/no) variable indicating whether the patient had more than one autograft procedure during the study (based on different dates on the same TW). Rates of patients with

more than one autograft procedure will be analyzed by displaying counts and percentages by treatment group (see Table 5). Furthermore, bar plots will be displayed. The proportion of patients with repeated autograft procedures will be compared between treatment groups using a chi square test (or Fisher's exact test in case of small estimated cell counts).

This analysis will be repeated on a wound level.

Area of repeated autografting

The area of repeated autografting per patient will be analyzed descriptively with number of units, number of missing values, mean, standard deviation, min, max, median and quartiles as shown in Table 4 and compared between groups with a one way analysis of variance. A graphical representation of the data will be done using histograms.

This analysis will be repeated on a wound level.

Early autografted wounds

A subgroup analysis will be performed on the subgroup of target wounds that are early grafted (for a definition see Appendix 13.1.1). The primary endpoint, the secondary endpoints "incidence of surgical excision" and "time to complete eschar removal", as well as the safety endpoint "time to complete wound closure" will be analyzed while only taking wounds that are early grafted into account.

Late autografted wounds

A subgroup analysis will be performed on the subgroup of target wounds that are late grafted (for a definition see Appendix 13.1.1). The primary endpoint, the secondary endpoints "incidence of surgical excision" and "time to complete eschar removal", as well as the safety endpoint "time to complete wound closure" will be analyzed while only taking wounds that are late grafted into account.

11.1.5.10. Duration of hospitalization

The duration of hospitalization will be analyzed descriptively with Kaplan-Meier plots (see Figure 3) and compared between groups with a log rank test.

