7.1. General Information of Trial Design

This is a multi-center, multi-national, randomized, controlled, assessor blinded, three-arm study aiming to demonstrate superiority of NexoBrid treatment over Gel vehicle control and over SOC treatment in thermal burn subjects with burns.

One hundred and seventy five subjects (175 subjects) are planned to be randomized to the study in a 3:3:1 ratio (NexoBrid: SOC: Gel Vehicle). The study will be conducted at sites in the US and out of the US.

Following the enrollment of a patient to the study and prior to randomization, physicians will identify one or more TWs per patient according to the TW definitions described in Section 1.1 of the protocol.

All subjects' DPT and FT burns that comply with the specified entrance criteria under Section 7.1.3 are intended to receive study treatment per the randomized study arm and therefore, must be designated as TWs. This will further allow an evaluation of the subject systemic safety by allowing treatment of the subject's entire deep burns as per the randomized study arm. After reviewing the entrance criteria, prior to randomization, eligible subjects will be stratified into different groups in order to standardize and minimize bias between study groups in terms of efficacy and safety outcomes that are expected to be correlated to the patient total burn area and its depth. Please refer to Section 13.7.1 of the protocol for full description of the randomization procedure.

Following the stratification, patients will be randomized as per their stratification group (see Section 11.1.10) in a 3:3:1 ratio (NexoBrid: SOC: Gel Vehicle).

Patients will be treated in the same way in all study arms (NexoBrid, SOC or Gel vehicle) except for the eschar removal stage which will be performed as per the randomization study arm.

Prior to initiation of eschar removal treatment subjects will be medicated with appropriate analgesia (please refer to Appendix 2- Pain Management Procedures of the protocol) and undergo wound cleansing and dressing of all wounds with antibacterial solutions (as specified

in Section 8.1 of the protocol). Following wound cleansing and antibacterial treatments, subjects will undergo the eschar removal process as per treatment assignment (NexoBrid, SOC or Gel Vehicle, following randomization) as further described in *APPENDIX 16- Treatment Diagram of the protocol*.

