7.3.4. Exploratory analyses

1. Reduction in surgical needs as measured by an analysis of % wound area surgically excised for eschar removal (and % TBSA excised of the treated TW) (tangential/ minor/ avulsion/ Versajet and/or dermabrasion excision),
2. Additional Cosmesis and Function evaluation will be performed using the Patient and Observer Scar Assessment Scale (POSAS) version 2.0 at 1, 3, 6, 12, 18 and 24 months after the wound closure confirmation visit by a burn wound specialist who is masked to randomized wound treatment and to the other outcome assessments of the same wound. POSAS version 2.0 was published in 2005 in Plast. Reconstr. Surg. 116: 514-522 by van de Kar et al. The POSAS consists of two parts: a Patient Scale and an Observer Scale. Both scales contain six items that are scored numerically and make up a 'Total Score' of the Patient and Observer Scale. The POSAS has been developed for all types of scars and has been tested in linear scars, burn scars and keloids and was found to be validated and reliable [27].

Each item of both scales has a 10-point score, with 10 indicating the worst imaginable scar or sensation. The lowest score is '1', and corresponds to the situation of normal skin (normal pigmentation, no itching etc). The score goes up to the worst imaginable. The Total Score can be simply calculated by summing up the scores of each of the six items. The Total Score will therefore range from 6 to 60 (observer and patient) and 12-120 in total.

POSAS will be evaluated for all measurement times mentioned above,

3. Additional Cosmesis and Function evaluation will be performed using the Modified Vancouver Scar Assessment Scale (MVSS) measurements obtained at 1, 3, 6 and 18 months,
4. Incidence of surgical Escharotomy procedures on circumferential extremities target wounds,
5. Incidence of reduction in interstitial/compartment pressure in circumferential extremity wounds (measured immediately following eschar removal),
6. Reduction in surgical need as measured by analysis of incidence of surgically harvested donor sites wounds,
7. Reduction in surgical need as measured by analysis of % area of surgically harvested donor site wounds,

8. Blood loss following eschar removal procedures using changes in Hematocrit following eschar removal procedures,
9. Cosmesis MVSS and POSAS will be used to assess the quality of the donor sites scars,
10. PK evaluation for a subset of NexoBrid patients (as described in section 11.21 of the protocol)

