11. Autograft related parameters.
 - 11.1. Efficacy and safety analyses for early and late grafted wounds (for definition see Appendix 13.1.1)
 - 11.2. Total number of target wound grafting procedures
 - 11.3. Incidence of repeated/additional grafting procedures
 - 11.4. Area of repeat grafting
12. Duration of hospitalization

8. Handling of protocol violations

Before database lock and statistical analysis, possible protocol violations will be discussed by data management, sponsor, PI and his/her proxy and the statisticians and classified as minor or major violations. The list with all protocol violations will be prepared by the data management.

A protocol violation will be classified as major if

- the treatment differs from the planned treatment (randomization arm), or
- the documentation of a primary observation was not done or is different from the study protocol: i.e. assessment was not done by a blinded assessor (assessment by blinded assessor from photos is acceptable), or
- there was drug misuse (this may include application time deviated in 25% or more, deviation of more than 20% in the TBSA area treated in one session at a time, if relevant, error in drug preparation (e.g. 2g mixed in 50g), storage temperature below - 2°C - 8°C or >24h at room temperature and used without any stability confirmation by sponsor), or
- the first blinded assessor was unblinded, or
- treatment started more than 5 days from injury, or
- one of the following inclusion criteria is violated:
 - Males and females; ≥ 18 years of age,
 - Thermal burns caused by fire/flame, scalds or contact,
 - Patient total burns area $\geq 3\%$ DPT and / or FT,
 - Patient total burns area should be $\leq 30\%$ TBSA; SPT, DPT and/or FT in depth,
 - Informed consent can be obtained within 84 hours of the burn injury
 - At least one wound (a continuous burn area) that is $\geq 0.5\%$ TBSA (DPT and/or FT) (this minimal wound size should not include face, perineal or genital)
 - Wound's blisters can be removed/unroofed, as judged by the investigator
- one of the following exclusion criteria is met:
 - Patients with burned charred fingers, 3rd degree in depth and possibly devoid of circulation
 - Patients with abraded wound/s that cannot be treated by an enzymatic debrider application (NexoBrid)
 - Patients with electrical or chemical burns
 - The following pre-enrollment dressings: a. Flammacerium, b. Silver Nitrate (AgNO_3)

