11.1.10. Stratification

The following factors are used to stratify the study design:

A. Total TBSA % per patient

A1: Total TBSA <=15%

A2: Total TBSA >15%

B. Overall depth per patient

B1: All TWs are full thickness;

B2: Mixed TWs – full thickness and deep partial thickness

B3: All TWs are deep partial thickness.

C. Center Group, to address possible differences in SOC procedures between sites (if any), to allow comparison of the results within group of centers and to reduce the likelihood of a group of centers including patients in only one arm of the study (5 groups of centers were formed based on similarity of SOC practice).

These factors are accounted for in the analyses of the primary and secondary endpoints by including them as adjusting variables.

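### Duration of hospitalization is compared with an unstratified log-rank test; the test is valid, but stratifying it by burn area and depth would probably recover power if those factors predict length of stay

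*SAP*

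**What the plan says.** Duration of hospitalization is the last item on the list of exploratory analyses in SAP section 7.3.4 ("12. Duration of hospitalization"). Section 10.3.5.16 defines it as the days from admission to discharge for the initial stay only. Section 11.1.5.10 says it is "analyzed descriptively with Kaplan-Meier plots (see Figure 3) and compared between groups with a log rank test". That section names no strata, no covariates and no effect estimate, and it does not say which of the three arms are compared.

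Section 11.1.10 lists the randomisation strata: total TBSA (up to 15%, above 15%), overall depth (all full thickness, mixed, all deep partial thickness) and centre group, where "5 groups of centers were formed based on similarity of SOC practice". Section 7.1 gives the reason for stratifying: "efficacy and safety outcomes that are expected to be correlated to the patient total burn area and its depth". Section 11.1.10 promises adjustment for these factors only for the primary and secondary endpoints.

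**The concern.** Two things happen when patients are randomised within prognostic strata and a log-rank test then ignores those strata. First, the arms are better balanced than the test's variance assumes, so the test rejects less often than its nominal level. Second, pooling patients with very different discharge rates pulls the overall hazard ratio towards 1. Both reduce power, and both grow with the strength of the strata.

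The plan's own premise is that burn area and depth relate to outcome, and length of stay is a natural candidate. If the premise holds for this endpoint, a real difference in stay between NexoBrid and SOC could be missed for want of a stratification that uses data already collected. At stake is the efficiency of one exploratory comparison, not its validity.

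**Working it through.** **The plan's own figures.** The SAP gives no effect size or power for length of stay. Its only time-to-event sizing is for time to complete eschar removal (section 9.3), and it reproduces:

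- Events: 4 × (1.96 + 1.28)² / 1.23² = 27.75, rounded up to 28, as stated.
- Patients: 2 × 28 / (0.595 + 0.728) = 42.3, so 22 per arm and 44 in total, as stated.

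**Inputs from the SAP.** 75 NexoBrid and 75 SOC patients (section 9.3.1); two-sided 5% level (section 11); 2 × 3 × 5 = 30 randomisation cells, of which TBSA × depth form 2 × 3 = 6.

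**Assumed inputs.** Every patient is discharged, giving 150 events and no censoring. The treatment hazard ratio is the one detectable with 150 events, exp(-(z for alpha + z for power) / √(150 × 0.25)):

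- 80% power: exp(-(1.96 + 0.84) / 6.12) = 0.63.
- 90% power: exp(-(1.96 + 1.28) / 6.12) = 0.589.

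Patients are split 80/20 by TBSA and 20/40/40 by depth, with equal centre groups. Stays are exponential, allocation is in permuted blocks of 2 within the 30 cells, and each setting has 4,000 runs. The Monte Carlo standard error of a power near 75% is √(0.75 × 0.25 / 4,000) = 0.7 points.

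**Results.** The strength column gives the discharge hazard ratio for TBSA above 15% and the ratio per step towards shallower depth.

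| Assumed strength | Type I error, unstratified | Power at HR 0.63: unstratified | 6 cells | 30 cells | Change, 6 cells vs unstratified |
|---|---|---|---|---|---|
| None (1; 1) | 5.1% | 80.4% | 76.8% | 66.7% | -3.6 |
| Weak (0.7; 1.25) | 4.7% | 76.8% | 75.9% | 65.7% | -1.0 |
| Moderate (0.5; 1.5) | 4.1% | 68.2% | 74.7% | 65.2% | +6.5 |
| Strong (0.33; 2.0) | 2.5% | 55.4% | 76.0% | 65.5% | +20.5 |

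At HR 0.589 the changes from unstratified to 6 cells, in the same order, are -2.9, 0.0, +5.9 and +19.4 points. If centre group also matters (hazard ratio 1.2 per level, with moderate TBSA and depth effects), the 6-cell gain is 6.8 points at HR 0.63 and 5.3 at HR 0.589.

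**A different outcome model.** This uses log-normal stays (log SD 0.55, treatment log ratio -0.25, 20% or 30% of patients above 15% TBSA, 2,000 runs) and compares the unstratified test with the 6-cell test:

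- No prognostic effect: 70–73% against 70–71%.
- Stay 1.5 times as long in larger burns, depth ratio 1.2 per level: 64–66% against 70–71%.
- Stay 2 times as long, same depth effect: 55–60% against 69–71%.
- Stay 2.5 times as long, same depth effect: 47–52% against 69–71%, a gain of about 20 points.

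A further log-normal run of the 6-cell test gave about -1 point with no effect, +1 to +2 if weak, +5 to +6 if moderate and +11 to +21 if strong. The unstratified test's type I error was about 2–4% under moderate to strong effects.

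**All 30 cells.** Using every randomisation cell gives 65–67% power at HR 0.63. That is below the unstratified test in every row except the strong one, because many cells hold too few patients to contribute a comparison. With a centre effect added to moderate TBSA and depth effects, the two are about equal (65.2% against 65.5%).

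**The case against.** The strongest reply is that the SAP contradicts nothing here. It promises adjustment for the strata only for primary and secondary endpoints. Length of stay is exploratory, outside the testing hierarchy of section 11.1.8, and described as a descriptive analysis. Most other exploratory comparisons in section 11.1.5 are also unadjusted, and the patient-level subgroup analyses in section 11.1.11 use plain log-rank tests. This is a consistent simplification, and that stands.

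It also stands that the SAP does not say how strongly area or depth predicts length of stay. Section 7.1 speaks of efficacy and safety outcomes in general. A reader might infer that power is certainly lost. The documents do not support that: with no or weak association the 6-cell test gains little or nothing and may lose about 3 to 4 points.

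Two further inferences fail. The unstratified test is not invalid, because its type I error stays at or below about 5%. Nor does time to complete eschar removal provide a model with these same strata. Its main analysis in section 11.1.3.2 is a Cox model with depth, TBSA, centre group and number of target wounds as covariates. Strata appear only in the fallback Wilcoxon-Gehan test, and there on all four variables.

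Finally, leaving out centre group although it is a randomisation factor is a judgement. The 30-cell results support it.

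**Conclusion.** The point holds as a minor, conditional efficiency improvement. The planned test is valid but becomes conservative, and probably less powerful, if burn area and depth predict length of stay. The trade-off is uneven: a cost of at most about 3 to 4 points if the factors are not prognostic, roughly nothing if weakly (-1 to +2), and a gain of about 5 to 7 points if moderately or 11 to 21 if strongly prognostic.

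These figures rest on 75 versus 75 patients, no censoring, and assumed treatment effects, stratum shares and strengths of association, none of which the SAP gives for this endpoint. The direction is the same under exponential and log-normal stays. No primary, secondary or other confirmatory conclusion depends on it.

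**What to change.** In section 11.1.5.10, specify NexoBrid versus SOC and use a log-rank test stratified by `tbsagroup` and `depthgroup` (6 cells). Do not add centre group. Keep the unstratified log-rank test as supportive, along with the Kaplan-Meier plots.

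If a hazard ratio is reported from the matching stratified Cox model, apply the proportional-hazards check already set out in section 11.1.3.2. This matters because hazards need not be proportional for length of stay.

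The cost is one STRATA line with the GROUP option, using variables section 11.1.3.2 already defines, and no new data. The downside is the possible loss of about 3 to 4 points of power if the strata turn out not to be prognostic. The choice should be fixed before the first-stage data are analysed.
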